3.2 Allocation to Treatment

Because our study is a repeated-measure, single subject experimental design with up to ten replications, there is no proposed plan or procedure for allocating study participants to various cohorts of arms of the proposed clinical investigation.

3.2.1 Randomization Procedures: N/A

3.2.2 Masking Procedures: N/A

• **3.2.3 Breaking the Mask**: N/A

4. SUBJECT SELECTION

4.1 Subject Inclusion Criteria

- 18 years of age or older with the ability to provide informed consent
- English as the primary language
- Medically and psychologically suitable
- Willing to receive/have received meningitis vaccinations
- Unsuccessful trial of non-invasive hearing amplification devices or tinnitus treatment as defined by standard of care of six months
- Able to pay for all care received through the study, either through the subject's insurance company or through self-pay
- Able to comply with study requirements, including travel to the investigational sites
- Severe to profound sensorineural hearing loss (\geq 70 dB thresholds between 500 and 4000 Hz) in the worse ear with \leq 20% CNC word scores
- Duration of single-sided deafness \geq one year
- Tinnitus localized to the affected ear, both ears or in the head localized to the affected ear, both ears, or in the head
 - Expected subjects include those with:
 - Unilateral hearing loss secondary to viral or bacterial infection, such as meningitis or labyrinthitis
 - Ménière's disease
 - Sudden sensorineural hearing loss
 - Vascular disease affecting the inner ear
 - A combination of any number of the above conditions

4.2 Subject Exclusion Criteria

- Duration of single-sided deafness \geq ten years
- Pure tone thresholds \geq 35dB at 500, 1000, 2000, and 4000 Hz in the better ear
- CNC word scores \leq 70% in the better ear

- Chronic otitis media in either ear •
- Inner ear malformation in either ear •
- Autoimmune inner ear disease (fluctuation sensorineural hearing loss in either ear) •
- Evidence of retrocochlear pathology, including vestibular schwannoma •
- Unilateral tinnitus in the unaffected ear •
- Cochlear ossification •
- Demonstrated cognitive and/or developmental challenges ٠
- Major depression or anxiety; post-traumatic stress disorder; substance abuse •
- Medical or psychological conditions that serve as contraindication to surgery •
- Additional handicaps that would prevent or limit participation in evaluations •
- Unrealistic patient or family expectations regarding the benefits, risks, and limitations inherent to the procedure and the prosthetic device
- Pregnant women: We will specifically ask all women of childbearing age if there is a • possibility they are pregnant or trying to become pregnant at the initial clinic visit; any women who are pregnant or actively trying to become pregnant will be excluded. In cases that are questionable on the day of planned surgery, a pregnancy test will be performed as per current MEEI anesthesia pre-operative protocols.

5. STUDY DRUG(S)/DEVICE(S)

5.1 Study Drug/Device Information

The MAESTRO Cochlear Implant system consists of a receiver/stimulator, a pocket sized speech processor worn on the body, and a microphone/headset. The system consists of an internal receiver/stimulator and an external audio processor. During surgery, a receiver/stimulator is implanted behind the ear. A wire leads from the receiver/stimulator to the nerve fibers of the cochlea. The audio processor picks up sound and transduces it into electrical impulses that are sent to the implanted receiver/stimulator. The impulse travels down the wire to the electrodes, which electrically stimulates the cochlea. This signal is transmitted through the auditory nerve to the brain.

The MAESTRO Cochlear Implant system is marketed under the brand name of MAESTRO Cochlear Implant and manufactured by MED-EL Corporation, USA (Durham, NC). The FDA has approved use of this cochlear implant device in patients with bilateral deafness.

5.2 Study Drug/Device Compliance/Adherence

Because the cochlear implant system is an implanted device, there are few concerns regarding compliance and adherence compared to most drug-based clinical trials. Our study is designed as a prospective, repeated-measure single subject trial. Participants in the experimental group will serve as their own controls. Throughout the study, we will confirm that subjects have been using the device through routine clinical follow-up and questionnaires at each appointment. Both qualitative and quantitative measures will be obtained to determine if subjects are benefiting from the cochlear implant system, and the individual activation parameters at each visit will be compared to the prior visit to ensure that settings on the device have not been altered or changed between visits.

Although we anticipate that the vast majority of subjects will derive a safe and substantial clinical benefit from use of the cochlear implant system, if a given subject is non-compliant or non-adherent with use of the cochlear implant system or external sound processor, then we will collect a final set of qualitative and quantitative measures and simply follow their outcomes through routine clinical exams. This approach will allow for monitoring of any

adverse safety or health concerns that may arise. Thus, no subjects in our study will be formally withdrawn for non-compliance or non-adherence and all study participants will be followed for one year after cochlear implant surgery. Any patient choosing to withdraw from the study will be replaced by a new study participant recruited from the clinic. The reasons for withdrawal or termination will of course be reported and documented at the time of occurrence.

If a subject withdraws or is terminated after implantation, a new subject will replace him or her. In principle, then, more than 10 subjects may end up with an implant based on their participation in the study.

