Cochlear implantation in SSD patients has also resulted in significantly improved sound localization and ability to hear in noise (Kamal et al., 2013). One important study examined SSD patients who were treated with cochlear implantation; the untreated side was either normal or treated with a hearing aid. The data demonstrated that, although there was a significant benefit in speech understanding and subjective quality of sound, sound localization only improved in patients with normal hearing on the opposite side (Vermeire and Van de Heyning, 2009). These findings are consistent with a more recent pilot study, in which three patients with short-term SSD and normal hearing in the other ear received a cochlear implant on the deafened side. These patients all achieved open-set speech recognition, improved sound localization, and improved word recognition in noise (Firszt et al., 2012). Another critical study evaluated SSD patients who had undergone cochlear implantation, comparing use of the cochlear implant to a CROS or BAHA. This study found that cochlear implantation resulted in significant gains with respect to objective sound localization and hearing-in-noise testing relative to the CROS or BAHA device in the same patients. Subjective and quality of life measures were also significantly improved with use of the implant (Arndt et al., 2010). Taken together, early data indicate that cochlear implantation in SSD can result in significant tinnitus suppression, improved sound localization and hearing-in-noise, and better quality of life overall.

2 Our hypotheses are that adult patients with postlingual, single-sided deafness who undergo cochlear implantation will 1) wear the implant full-time, 2) report that the cochlear implant provides benefit, 3) show improvement in speech comprehension in quiet and in background noise, 4) demonstrate an improvement in sound localization, and 5) report a reduction in the frequency and intensity of tinnitus compared to before

surgery. To test these hypotheses, we will formally and systematically test patients both before and after surgery as detailed below.

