Approximately four weeks post-operatively, subjects will be fitted with an approved MED-EL Sound Processor and initial stimulation will take place. The following procedures will occur at this visit:

- Modified Hearing Handicap Inventory and Quality of Life (SF-36) questionnaires will be administered (see attached)
- Detection measures
- Psychophysical measures
- Safety measures

Three, Six, and Twelve Months Post-activation Visits (to MEEI):

The following procedures will occur at all these visits unless otherwise specified:

 Modified Hearing Handicap Inventory and Quality of Life (SF-36) questionnaires will be administered (see attached)

- Pure tone threshold audiometry at each post-activation interval
- Word recognition testing at each post-activation interval
- Tinnitus assessment at each post-activation interval, along with ABR testing at the six month mark
- Psychophysical measures at each post-activation interval
- Safety measures at each post-activation interval

Visit to University of Wisconsin – Madison after Twelve Months Post-activation:

Once time has been established to acclimate to the cochlear implant, subjects will undergo study-related spatial hearing testing in addition to clinical follow up visits. Depending on subject availability in schedule, the following procedure will take place unless otherwise specified:

 $\cdot\,$ Spatial hearing testing at the Binaural Hearing and Speech Lab at UW – Madison ([name] lab)

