8.2 Effectiveness Assessments

Effectiveness assessments will be completed based on audiologic testing and subjective questionnaires at each follow-up appointment. These will be compared to the subjects' preoperative baseline measures. In particular, primary dependent measures will include:

- Pure Tone Threshold Audiometry
- Sound Localization Testing (University of Wisconsin Madison)
- Speech Perception Measures Consonant-Nucleus-Consonant (CNC) Testing
- Psychophysical Measures
- Tinnitus Assessment Tinnitus Handicap Inventory (THI)
- Subjective Questionnaires Hearing Handicap Inventory, Abbreviated Profile of Hearing Aid Benefit (APHAB) questionnaire, Speech Spatial and Qualities of Hearing Scale (SSQ), and Quality of Life (SF-36) questionnaire

Each CI subject's speech perception ability will be ranked on a continuum of performance by using standardized speech perception tests that document the range of perception abilities. We will use the Consonant-Nucleus-Consonant (CNC) test (House Ear Institute). The CNC open set single-syllable test will be administered and scored both for whole-word and phonemic items. All speech tests will use recorded materials at a level of 65dB HL and will be presented in the soundfield through a speaker to the subject at 0 degree azimuth and calibrated at a set

distance, typically 1 meter. We will test SSD patients in the bilateral condition, using the good ear only and use contralateral masking to eliminate contributions from the good ear to evaluate the implanted ear.

Each subject's spatial hearing ability will be assessed in collaboration with [name] at the University of Wisconsin. Subjects will identify a single word randomly chosen from a set of fifty possibly alternatives and presented from a loudspeaker directly in front of the subjects. Speech intelligibility will be tested by masking sentences co-presented at different spatial configurations. The presentation level of the target speech will be varied in order to generate different signal-to-noise ratios at each condition. We will evaluate implanted SSD patients with the device turned on and off to directly evaluate contribution of the cochlear implant to understanding speech-in-noise.

Recorded test materials, test keys and patient response forms will be collected and documented as part of the study. Number of test items and percentage scores on each test will be documented and included in the data analysis.

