13. STUDY DISCONTINUATION CRITERIA

13.1 Discontinuation of Individual Research Subjects

As described, safety measures will include complications questionnaires and frequent postoperative follow-up visits. Inquiries about both major and minor complications will be made and any complications will be recorded. A research assistant will regularly review safety measures every month for all study participants and discuss any safety concerns/adverse outcomes with the investigator. The investigator will then decide whether the research study should be altered or stopped. If a clear answer is not evident, the investigator will discuss the safety concern with the Human Studies Committee and make appropriate adjustments to the study as needed. Other discontinuation criteria are described under Section 5.2 (Withdrawal of subjects due to non-compliance/adherence) and section 9.3 (Withdrawal of subjects due to adverse events) of the clinical protocol.

If withdrawn subjects agree to measurements of clinical outcomes and assessments of device safety, their data will be collected until one year following cochlear implantation surgery. As with other criteria for withdrawal, subjects that are withdrawn will be replaced through recruitment of additional study participants in clinic.

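### Section 5.2 does not secure the post-operative Wisconsin spatial test for subjects who stop using the implant, so a primary measure can be missing selectively in non-users

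*Combined protocol and SAP*

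**What the plan says.** Section 1.2 hypothesises that adults who "undergo cochlear implantation will 1) wear the implant full-time, 2) report that the cochlear implant provides benefit". Better sound localization is the fourth hypothesis.

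Section 5.2 checks use throughout: "we will confirm that subjects have been using the device through routine clinical follow-up and questionnaires at each appointment". If a subject is not using the device, the rule is "we will collect a final set of qualitative and quantitative measures and simply follow their outcomes through routine clinical exams". The reason given is to watch for safety and health problems. The section then states that "no subjects in our study will be formally withdrawn for non-compliance or non-adherence and all study participants will be followed for one year", counted from surgery. It names no assessments for that year.

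Section 8.2 lists Wisconsin sound localization among the primary dependent measures. Section 3.1 says that, after a period of acclimatization, "subjects will undergo study-related spatial hearing testing in addition to clinical follow up visits". It lists one post-operative Wisconsin visit, after twelve months post-activation and dependent on the subject's availability.

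Section 13.1 collects data to one year after surgery from withdrawn subjects who agree. It refers to 5.2 as a section on withdrawal for non-adherence, and adds that "subjects that are withdrawn will be replaced through recruitment of additional study participants in clinic".

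Section 10.4 analyses data from all participants and keeps what was obtained from those who withdraw. Section 10.5 analyses each subject individually. Neither has a rule for missing 12-month or spatial values.

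**The concern.** A subject who stops wearing the implant is among those least likely to have benefited. Section 5.2 moves that subject from the study schedule to routine exams. The outcomes at risk are those that routine care does not supply, and the Wisconsin test is the clear case: it is study-related, done in another city, and listed only once after surgery. If it is missed, no other post-operative value takes its place. Hypothesis 4 would then be judged mainly on continuing users, and spatial benefit in the implanted group could look better than it was.

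**Working it through.** The plan has no figure to reproduce. Section 10.3 gives ten subjects, with no effect size, standard deviation, numeric power, dropout allowance or non-use rate. The check is therefore mainly a comparison of the texts.

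**Step 1. What a non-user still has under 5.2**

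| Outcome | Text that bears on it | Position |
|---|---|---|
| Audiometry, CNC words | 7.4 and 13.2 treat audiologic testing as standard or routine care | Probably continues |
| Questionnaires, THI at 12 months | 8.2 places questionnaires before each follow-up appointment; 5.2 follows everyone for one year | Probably covered, but 5.2 does not say so |
| Device use | 5.2 checks it at each appointment | Known |
| Wisconsin spatial test | 3.1 makes it additional to clinical visits; nothing puts it in the final set or routine exams | Not secured |

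The row labels of the schedule of events are not readable in the copy reviewed, so it cannot settle the last line. That is not a fault of the plan.

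**Step 2. Does the one-year follow-up reach the Wisconsin visit?**

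Inputs: activation at two to three weeks after surgery, or about four weeks (both in 3.1); a visit window of plus or minus four weeks (7.5); follow-up of one year from surgery (5.2, 13.1), taken as 52 weeks.

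- Weeks from surgery to twelve months post-activation = activation week + 52.
- Earliest activation: 2 + 52 = 54. Latest: 4 + 52 = 56.
- With the window: 54 − 4 = 50 to 56 + 4 = 60.

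The Wisconsin visit comes after that point, so it nominally falls beyond week 52. The 12-month clinic assessments may fall on either side.

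**Step 3. Effect on the planned analysis**

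If k of ten subjects lack the post-operative spatial test, 10 − k individual pre/post results remain: 9 for k = 1 and 8 for k = 2.

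**Step 4. Illustration for a group mean, which 10.5 does not specify**

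Assume that the missing subjects' change is f times the mean change of the others. The overstatement of the mean is 10 / ((10 − k) + k·f) − 1.

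| f (assumed) | k = 1 | k = 2 |
|---|---|---|
| 0 (zero change) | 10/9 − 1 = 11% | 10/8 − 1 = 25% |
| 0.5 | 10/9.5 − 1 = 5% | 10/9 − 1 = 11% |
| 1 (same as the others) | 0% | 0% |

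**Step 5. Could it arise among ten subjects?**

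The chance of at least one non-user is 1 − (1 − p)^10. For assumed non-use rates p of 5%, 10% and 20%, this is 40%, 65% and 89%. The rates are assumptions, and not every non-user would miss the test.

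**The case against.** The strongest reply is that the plan already intends to keep these subjects. Section 5.2 withdraws nobody for non-adherence and follows everyone for one year. Section 13.1 collects outcomes to one year even from withdrawn subjects who agree, and it would be odd to give less to non-users who stay in the study. Section 10.4 analyses all participants. The final set is also not empty: 7.1, 7.2 and 8.2 link qualitative measures to questionnaires and quantitative measures to audiologic tests. Finally, the Wisconsin visit depends on availability for every subject, so loss is possible in anyone.

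Much of this stands. It answers most of the concern about audiometry, CNC, questionnaires and THI. It does not answer the concern about the spatial test: the one-year sentences name no assessments and nominally end before the Wisconsin visit, and 10.4 cannot analyse a value that was never collected. The availability condition makes loss possible for all, but only non-users have a rule that moves them to routine exams.

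Three stronger readings are tempting, and the documents do not support them:

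- A reader might infer that non-users are withdrawn, replaced and dropped from the results. Section 5.2 says they are not withdrawn for non-adherence, 10.4 keeps all participants' data, and the contrary wording in 13.1 is mainly a loose cross-reference.
- A reader might infer that the rate of full-time use is itself inflated. Use is checked at each appointment, and under 10.4 known non-users should already count.
- A reader might take the percentages above as the bias in this trial. They describe a group mean that the plan does not specify, under assumed numbers and assumed change.

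**Conclusion.** The point holds for the post-operative Wisconsin spatial test. Followed as written, the plan can leave a non-user with no post-operative result on a primary dependent measure, and such losses would fall on the subjects least likely to have benefited. For the 12-month questionnaires and THI it is a matter of clarity, since they are probably covered. It does not extend to audiometry or CNC.

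The size is unknown. In the subject-by-subject analysis the cost is one spatial result of ten per missing subject. The bias in any summary depends on two things the documents do not give: how many subjects stop use and miss the test, and how their change would compare with that of the others. If it would have been the same, there is no bias. The gap is preventable at low cost and should be closed.

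**What to change.** - **5.2:** State that non-users who agree stay on the existing study assessments through month 12 and the Wisconsin visit, with device use recorded at each test. Say when the final set is taken and which tests it contains.
- **13.1:** Correct the cross-reference so that it agrees with 5.2 on non-adherence.
- **10.4:** It already includes all participants. Add that replacements are additional to the original subjects and do not substitute for them, that known non-users count as not full-time users, and that the number of and reasons for missing 12-month and Wisconsin values are reported. A sensitivity analysis that sets missing spatial change to zero is optional.

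The cost is protocol wording, a few extra tests per non-user, and one trip that the collaborating laboratory already funds (2.1, 7.2). Testing with the device on and off (8.2) already suits a non-user. Some will decline to travel, so some values will stay missing, and the results may look less favourable.

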5.3 Study Drug Supplies

The MAESTRO Cochlear Implant system is already FDA-approved for use in patients with bilateral deafness. As with other cochlear implants, the MAESTRO Cochlear Implant device is ordered prior to surgery. As the MAESTRO Cochlear Implant System is already being used in patients with bilateral deafness, standard storage, dispensation, handling, and disposal protocols are already in place. Similar protocols will be used in our study. In particular, upon receipt the device will be kept in storage with other electrical implant devices at MEEI, and at the time of surgery, dispensed/opened and subsequently handled with appropriate sterile technique.

5.4 Study Drug/Device Storage and Accountability

The cochlear implant system is stored at room temperature upon receipt and kept securely until it is used during surgery. Cochlear implants utilized for this study will be kept separate from devices for clinical use within device locked storage. Given its electronic components, prolonged exposure to extreme temperatures should be avoided. In our study, the cochlear implant system will be kept in storage with other electrical implant devices at MEEI, and at the time of surgery, dispensed/opened and subsequently handled with appropriate sterile technique. Nearly all aspects of the device are implanted in the patient (with the exception of the speech processor and microphone/headset, which are worn externally). The device contains a few disposable components, which are primarily used to accurately place the device intra-operatively. These components will be disposed of in biological waste containers during the surgery. Because the MAESTRO cochlear implant system is an implanted device,

protocols for the proper destruction or disposition of study devices upon completion or termination of the clinical research are not necessary.

5.5 Other Medications

Our study does not include the planned use of other medications concomitantly with the MAESTRO Cochlear Implant. If patients experience complications or medical concerns related to the cochlear implant device, these will be handled appropriately through routine medical management in the Otology clinic or appropriate referral to other providers. There are no specific medications that are not allowed in participants of our clinical research study. In addition, rescue medication or therapies will not be used in this study.

